**SfE CORE Study Protocol**

**STUDY SUMMARY**

Study Title	SfE CORE study: Clinical Observations and Research on Engagement in Specialist Weight Management Services.
Internal ref. no. (or short title)	SfE CORE Study
Study Design	Observational cohort study
Study Participants	Patients attending Specialist Weight Management Services (or equivalent services) NHS obesity clinics in England and Wales.
Planned Size of Sample (if applicable)	To get half of the weight management services to collect data from 60% of patients attending their weight management service.
Follow up duration (if applicable)	For as long as in the weight management service, average time for this is 18 months.
Planned Study Period	48 Months
Research Question/Aim(s)	To understand the demographic and clinical characteristics of the people who attend the specialist weight management services and how they respond to the treatments that they are offered.

**FUNDING AND SUPPORT IN KIND**

FUNDER(S)	FINANCIAL AND NON FINANCIAL SUPPORT GIVEN
Novo Nordisk	Education grant to do study in weight management
Rhythm Pharmaceuticals	Education grant to do study in weight management
Boehringer Ingelheim	Education grant to do study in weight management

**ROLE OF STUDY SPONSOR AND FUNDER**

The Society of Endocrinology is the sponsor of the study. The sponsor will be responsible for initiation and management of the study, and the data ownership. Though, the sponsor controls the final decision regarding these aspects of the study. The sponsor will help with dissemination of the results.

Novo Nordisk, Rhythm Pharmaceuticals and Boehringer Ingelheim have provided financial support for this study. They will not play a role in data analysis interpretation, manuscript writing or dissemination of the results. Support from these companies will be acknowledged in manuscripts resulting from this work.

**SfE CORE Study Protocol**

**ROLES AND RESPONSIBILITIES OF STUDY MANAGEMENT COMMITTEES/GROUPS & INDIVIDUALS**

On this project there will be a Study steering committee and patient and public involvement group.

The study steering committee, chaired by a Consultant Endocrinologist, will meet up to 3-4 times a year to:

- Suggest any changes to the data being collected (which if made will be made after ethical approval).
- Suggest sites which would be suitable to participate in the collation of data
- Sign off on the yearly annual report.
- Determine who is able to have access to the anonymised data generated by the Database
- Consider whether additional projects can be tied to this database.
- Oversee the management of the budget for the project provided by external funders, held at the Society for Endocrinology

The patient and public involvement group will meet two times a year to:

- Suggest any changes to the data being collected or the way in which we do this if patients are describing difficulty with using the app (which will only be after ethical approval).
- Suggest what changes could be made to our method of recruitment if we are struggling to engage patients.
- Help with news letters to patients involved in the study.
- Comment on the yearly annual report.
- Comment on any results that are obtained.
- Help with publications and producing literature explaining the results of the study to patients and the public.

**PROTOCOL CONTRIBUTORS**

[figure not shown]
This protocol has been designed with help of the study steering committee, South East London Patient Support Group, and the study sponsor. The funders have had no role in designing the protocol.

**KEY WORDS:**

Obesity  
Specialist weight management services  
Observation study  
Clinical outcomes  
Patient reported outcomes

SfE CORE Study Protocol

**STUDY FLOW CHART**

SfE CORE Study Protocol

### 1 BACKGROUND

Obesity is an escalating issue in the UK, which currently has the highest obesity rate in Europe [1]. Approximately 27% of the adult population is classified as obese, contributing significantly to the primary care workload, with obesity associated with 44% of Type 2 diabetes cases, 23% of ischaemic heart disease cases, and 41% of certain cancer types [2]. Notably, the prevalence of severe obesity—an important factor in reduced life expectancy—has doubled over the past decade, affecting approximately 2.6 million adults [2].

The current framework for obesity management in the UK consists of a four-tier model. Tier 1 focuses on prevention and is managed by Public Health initiatives. Tier 2 services are community-based, providing referrals to evidence-based lifestyle interventions such as Weight Watchers and the Counterweight Programme. Individuals in Tier 2 typically have a BMI of 28-35 and do not present with complex medical issues. Tier 3 services or specialist weight management services represent a multidisciplinary specialist approach, available in community, primary or secondary care settings. This tier caters to individuals with a BMI greater than 35 (or over 30 if they have diabetes) and complex medical conditions, offering pharmacotherapy, low-energy liquid diets, and pre- and post-bariatric surgery care. Tier 4 services, located within secondary care, focus on bariatric surgery.

Data on obesity rates are systematically collected by the National Audit Office, enabling monitoring of Tier 1 effectiveness. Additionally, the National Bariatric Database provides insights into bariatric surgery rates, patient characteristics, and surgical outcomes [3]. However, comprehensive data on Tier 3 or specialist weight management services remain scarce, with information primarily available from only 4 of the 42 tier 3 clinics. Consequently, it is challenging to ascertain the availability of Tier 3 services across different regions, the volume of referrals, the demographics of individuals accessing these services, and their outcomes during treatment. This lack of data hinders our ability to evaluate equitable access, appropriate referrals, and the overall effectiveness of these services throughout the UK.

#### Objectives of the CORE Study

Our primary objective is to establish a study that will compile data from weight management services, focusing on the following key areas:

1. **Demographics:** Age, sex, socioeconomic status (derived from postcode), ethnicity, marital status and employment status and Job.
2. **Weight History:** Weight at significant life milestones (birth and leaving school), onset of weight issues, highest and lowest adult weight, weight changes over the past five years.
3. **Previous Weight Loss Attempts:** History of interventions and weight loss with these.
4. **Medical Conditions:** List of medical conditions with dates started. Severity of these medical conditions will be assessed using the Kings score and Edmonton score.
5. **Medication:** Details on dosage and frequency and when started on these drugs.

#### SfE CORE Study Protocol

6. **Patient-Reported Outcomes:** Quality of life (EQ5D questionnaire) and well-being (BodyQ questionnaire).
7. **Clinical Treatments:** Interventions received during clinic visits.
8. **Clinical Measures:** Weight, height, BMI, blood pressure.
9. **Relevant Laboratory Results:** HbA1c if has diabetes.

The information gathered through this study will serve to enhance productivity in existing services, inform business planning, and support the establishment of new services. It will also provide critical data to ensure equitable access to weight management services nationwide. Furthermore, the database will function as a registry, enabling researchers to apply for access to data that will advance our understanding and treatment of obesity.

**Study Aim:** This study aims to demonstrate proof of concept for our new data collection system involving a network of weight management clinics across England and Wales. Success would be seen in getting 50% of the current specialist weight management services (there are approximately 49 services at the moment[4]) to capture data on 60% of the patients attending their clinics. Focusing on specialist weight management services in the first instance and then rolling out to other primary care services in a second phase.

## 2 RATIONALE

As mentioned above there is very little data on who attends specialist weight management services and how effective the interventions offered in these clinics are. This study will enable us to say

1. Whether there is equal access to treatment based on sex, age, social class and ethnicity and if not start to work out what we can do to ensure this does happen.
2. The characteristics of the people attending the specialist weight management services. This data will give an insight as to how unwell this population is and how many people are being referred to these services which will help with planning of services.
3. How effective these services are and whether this varies from area to area. If we find specific models that are working well we can highlight these to the other clinics.
4. Some insight into the “real world” effectiveness of different types of interventions. This is particularly important with two new obesity drugs now being offered on the NHS.

## 3 RESEARCH QUESTION/AIM(S)

This study aims to demonstrate proof of concept for our new data collection system involving a network of specialist weight management service across England and Wales. Success would be seen as getting 50% of the current specialist weight management services [4] to capture data on 60% of the patients attending their clinics

### 3.1 Objectives

1. To get 50% of specialist weight management services that exist in England and Wales to collect data on patients that attend their weight management clinics.

#### SfE CORE Study Protocol

2. For the centres entering data to capture data on 60% of the patients attending their clinics.
3. To compare the data entered by 100 patients to that collected by a doctor in their initial interview. This will validate that data entry by patients is reliable.
4. To demonstrate that key outcomes are captured in sufficient quantity to give a fair representation of the people attending the clinics.
5. To describe the demographics and clinical characteristics of people attending the specialist weight management services who sign up to the study.
6. To look at changes in weight and well-being over the time in clinic and whether this is affected by treatment modality.
7. To explore potential disparities in access to specialist weight management services based on demographic factors (e.g., ethnicity, socioeconomic status).
8. To explore potential disparities in outcomes from specialist weight management services based on demographic factors (e.g., ethnicity, socioeconomic status).
9. To explore this methodology in collecting data on these characteristics from those patients who attend weight management services in primary care settings.

### 3.2 Outcomes

	Objectives	Outcome Measures	Timepoint(s)
Primary	To demonstrate that our system can be integrated into specialist weight management services clinics and collect data on patients attending clinics.	The number of clinics using the system by end of year 2 of the project. Our aim would be to have 50% of specialist weight management services using this system.	24 months
Secondary	To demonstrate that key outcomes are captured in sufficient quantity to give a fair representation of the people attending the clinics	That the clinics on average are collecting data on 60% of the patients that attend their clinics and on these they have at least 80% data on our key outcomes which are  Demographics Age, sex, socioeconomic status, ethnicity, marital status and employment status and Job.	Baseline  Baseline

SfE CORE Study Protocol

		
Weight history Birth weight, age weight problem started at, highest and lowest weight. Current weight.
 
Previous Weight Loss Attempts Previous Bariatric surgery – Y/N – if Y when and Type. Attempts at commercial diets – Y/N if Y when and Type Tried weight loss medication – Y/N if Y when and Type
 
Medical and drug history List of medical problems with date started. List of drugs taking with dose, frequency and start date.
 
Clinical Treatments Diet and Exercise advice Y/N if yes details and date offered Low calorie diet Y/N if yes details and date started and finished. Specific help with eating habits Y/N, If yes details and date (S) delivered Sessions with psychologist Y/N, If yes details and date (s) delivered. Weight loss drugs Y/N if yes which type and when started. Referred for surgery Y/N if yes when.
 
Patient-Reported Outcomes EQ5D and Body Q
 
Clinical Measures Weight, height, BMI, blood pressure.
	
Baseline
 
Baseline and every 12 months until leaves clinic.
 
Baseline and every 12 months until leaves clinic.
 
Baseline and every 12 months until leaves clinic.
 
Baseline and every 12 months until leaves clinic.
 
Baseline and every 12 months until leaves clinic.
 
Baseline and every 12 months until leaves clinic.

--	--	---	---

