#### Data collection

Patients will be recruited from weight management services, specialist weight management service in the first instance, via informed electronic consent. Those patients interested in being involved with the study will download an app (*PeopleWith*). Through this app they will learn more about the study and consent to be involved. Once they have consented to being involved, they will be asked to fill in demographic and clinical data on the app and complete some questions. The following data will be collected.

1. **Demographics:** Age, sex, socioeconomic status (derived from postcode), ethnicity, marital status and employment status and Job.
2. **Weight History:** Weight at significant life milestones (birth and leaving school), onset of weight issues, highest and lowest adult weight, weight changes over the past five years.
3. **Previous Weight Loss Attempts:** History of interventions and weight loss with these.
4. **Medical Conditions:** List of medical conditions with dates started. Severity of these medical conditions will be assessed using the Kings score and Edmonton score.
5. **Medication:** Details on dosage and frequency and when started on these drugs.
6. **Patient-Reported Outcomes:** Quality of life (EQ5D questionnaire) and well-being (BodyQ questionnaire).
7. **Clinical Treatments:** Interventions received during clinic visits.
8. **Clinical Measures:** Weight, height, BMI, blood pressure.
9. **Relevant Laboratory Results:** HbA1c if has diabetes.

Every 3 months patients will be prompted to update their records. Patient reported outcomes will be repeated every 12 months or when treatment is changed. See table below explaining in more detail about how the app collects data.

App Registration	New Symptom/Treatment Added	Notifications to Patients
Upon registration there will be a series of mandatory health related data points for the patient to complete	If a patient adds in a new symptom or treatment this will trigger the opportunity to complete a new EQ5D and BodyQ.	Patients will be reminded by notification of the mandatory data points if they have not been completed within 2 weeks of registration
Upon registration there will be available health related data points which are not mandatory for the outcomes of the project, however, there is the opportunity for the patients to		If a patient adds in a new symptom or treatment this will trigger the opportunity to complete a new EQ5D and BodyQ.

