#### Data analysis

The primary outcome of this study is the number of clinics collecting data. Our aim is to get 50% of specialist weight management service using the database. We will report the number of specialist weight management service and what percentage of clinics are using the app at year 2 of the project.

The secondary outcomes of this study are the percentage of patients who we capture data on, and the percentage of data captured on key variables. Our aim to capture data on 60% of patients who attend the services and of those who sign up to the study aim to capture key data on 80% of these patients. The percentage of people we capture the data on will be = (the number of people we have data on/the number of people who attend the clinic) X 100. The percentage of key variable will be worked out for each variable and will be = (number of variable entered/ number of variable possible) x 100.

For the exploratory analysis we will use simple stats (mean, median, SD, interquartile ranges and percentage) to describe the demographic and clinical characteristics of the people entered into the database. Multivariable linear regression will be used to look at the change in weight, BMI, EQ5D and Body Q scores over 12 months and to determine if this is influenced by treatment modality and demographic groups. All analysis will be done in STATA.

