#### SfE CORE Study Protocol

in scope, falling short of achieving a comprehensive national overview. Should this project succeed in gathering adequate data, this system will be commissioned as the NHS-standard platform for such data collection.

Our target is to engage 50% of specialist weight management service to use this system and capture 80% of essential data points for 60% of patients attending these clinics. Each weight management service typically receives approximately 700 patient referrals annually, with patients spending an average of 18 months in the program. We plan to recruit patients for two years, tracking outcomes for the duration of their clinic attendance. Data entry can be retrospective, allowing us in the first year to gather data on approximately 1,050 existing patients ( $700 \times 1.5$ ) and 700 newly referred patients each in the first and second years, leading to a potential recruitment of 2,450 patients per service.

Assuming an 80% capture rate, we anticipate enrolling 1,960 patients per clinic, resulting in a total of 41,160 patients across 21 participating sites.

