#### SfE CORE Study Protocol

- Sites will be required to keep a secure screening log of the patients as the data inputted into the platform will be anonymised by a patient identifier.
- Patients will input their own patient related data into the app when they see fit.
- The *PeopleWith* App user or 'Patient' acts as the owner and controller of their own data. The patient is at the centre and provides their own consent regarding sharing of their Health Data.
- *PeopleWith* acts as Data Processor as defined in the General Data Protection Regulation (GDPR).
- The *PeopleWith* Platform and App have been built from the outset using the core principle of information security; confidentiality, integrity and availability. Day to day implementation of 5 key information security protocols to mitigate risk of breach of data and system security, including remote access, password management, USB devices, acceptable use policy, routine system monitoring. Data Encryption, user access authentications, and other technical measures are in place to ensure data protection.
  - Backups occur every 24 hours and are stored in a dedicated secured, single tenant, blob storage cloud-based environment with limited access. The national clinical data collected has the potential to be layered with the patient collected data via the patient's screening number. The Society for Endocrinology will own and be the controller of the combined data in its anonymised format. *PeopleWith* will act as the data processor.
  - In the unlikely event that the *PeopleWith* platform can no longer be utilised for data storage, all data from the CORE Study will be moved to an alternative database held securely at the Society for Endocrinology

Data will be retained for 10 years. The study will contain identifiable data including name, date of birth and first section of postcode. The samples collected during the course of the data collection will be standard care only so there are no samples collected and stored on behalf of the study.

Patients will be asked to complete a quality of life questionnaire at every 6 months or if they have entered a new treatment or symptom.

As the patient identification key is recorded and made evident in the platform as well as recorded on the screening logs

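### The primary outcome counts clinics using the system with no minimum capture, and 60% capture is judged as an average, so both targets can be met without the stated success rule being met

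*Protocol*

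**What the plan says.** **Aim.** The study aim in section 1 and the aim in section 3 define success in one sentence with two parts: "getting 50% of the current specialist weight management services [4] to capture data on 60% of the patients attending their clinics". The study summary says much the same. Section 3.1 lists the parts as separate objectives: objective 1 is half of services collecting data, and objective 2 is that centres entering data reach 60% of their patients.

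**Primary outcome (section 3.2).** "The number of clinics using the system by end of year 2 of the project", with a target of 50% of services at 24 months. Section 4, Data analysis, restates it as the number of clinics collecting data and reports the percentage using the app. Neither place says what counts as use.

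**Secondary outcome (section 3.2).** "That the clinics on average are collecting data on 60% of the patients that attend their clinics", with at least 80% data on the key outcomes for those patients. Section 4 gives the capture percentage as people with data divided by people attending, times 100.

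**The 80% target elsewhere.** Section 4 says "of those who sign up to the study aim to capture key data on 80% of these patients", then gives a percentage for each variable, with the number of entries possible as its denominator. Section 6.2.1 says "capture 80% of essential data points for 60% of patients attending these clinics".

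**Questionnaire interval.** Section 4, Data collection, says "Patient reported outcomes will be repeated every 12 months or when treatment is changed". The outcome table and the schedule in Appendix 2 also give 12 months. Section 7.6, Data Recording and Record Keeping, says "Patients will be asked to complete a quality of life questionnaire at every 6 months".

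**The concern.** The aim asks for breadth and depth together: enough services, and enough patients within each. The primary outcome keeps only breadth. A clinic that has entered one patient counts the same as a clinic that has entered most of its attenders. The secondary outcome does not restore the missing condition, because an average lets high-capture clinics offset low-capture ones. No stated outcome counts the services that individually reach 60%.

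Wide sign-up with thin enrolment is the failure that the 60% condition is there to detect. As the outcomes stand, the same data could be reported as success or failure depending on which reading is chosen, and that choice could be made after the data are seen. The same holds for completeness, where the wording of the 80% target and the number of questionnaires due both vary by section.

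**Working it through.** **The plan's own figure.** The only computed figure is the projected enrolment in section 6.2.1: 700 × 1.5 + 700 × 2 = 2,450 per service; 2,450 × 0.80 = 1,960; 1,960 × 21 sites = 41,160. It reproduces exactly, but says nothing about how capture is spread over services, so the point does not rest on it.

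**Inputs.** About 49 services (section 1, study aim); target 50%; capture threshold 60%. The protocol gives no between-clinic spread, so every spread below is an assumption.

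**Step 1: services needed.** 0.50 × 49 = 24.5, so 25 services meet the primary target (25/49 = 51%). The number of these that must reach 60% capture for the primary outcome is zero.

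**Step 2: add the secondary target.** Let 25 clinics use the system with mean capture of exactly 60%, and count those at or above 60%.

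| Capture pattern (assumed) | Mean | Clinics ≥ 60% | Share of 49 |
|---|---|---|---|
| All 25 at 60% | 60% | 25 | 51% |
| 12 at 80%, 1 at 60%, 12 at 40% | (9.6 + 0.6 + 4.8)/25 = 60% | 13 | 26.5% |
| 5 at 100%, 20 at 50% | (5 + 10)/25 = 60% | 5 | 10% |
| 1 at 84%, 24 at 59% | (0.84 + 14.16)/25 = 60% | 1 | 2% |

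At least one clinic must be at or above 60% if the mean is 60%, so 1/49 is the floor and 25/49 the ceiling.

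**Step 3: a smooth spread.** A beta distribution stays within 0 to 100% and can hold the mean at exactly 60%. Its parameters are 0.6n and 0.4n, with n = 0.6 × 0.4/SD² − 1. For SD 0.05 to 0.25, the expected share of using clinics at or above 60% is 50.6% to 53.3%. Multiplied by 25/49, that is 25.8% to 27.2% of services.

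**Step 4: the other service count.** The background also mentions 42 clinics. Half is 21. The range becomes 1/42 = 2% to 21/42 = 50%, with 11/42 = 26% for a symmetric split.

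**Step 5: averaged or pooled.** Take one clinic with 1,000 attenders at 40% and one with 200 at 80% (assumed sizes). The clinic average is (40 + 80)/2 = 60%. The pooled figure is (400 + 160)/1,200 = 47%. The formula in section 4 does not say which is meant.

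**Step 6: completeness.** If every variable reaches 80%, the overall share of data points does too, but the converse fails: well-filled items can hide one that is mostly missing. The wordings in sections 3.2, 4 and 6.2.1 are therefore not interchangeable. The number of scheduled follow-up questionnaires is 24/12 = 2 or 24/6 = 4 over 24 months. Over the stated 18-month average stay it is 1 or 3. The denominator changes with the section consulted.

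**The case against.** The strongest reply is that the aim need not be read service by service. The protocol lists two separate objectives, measures the second on average, and in section 6.2.1 speaks of 60% of patients attending these clinics, which can be an aggregate. On a clinic-average reading, meeting the primary and secondary targets together does meet the aim. Adoption first and capture second is also a legitimate ordering for a feasibility study. This stands in part: the aggregate reading is possible. But section 3 and objective 2 more naturally describe what each service does, and on either reading the primary outcome carries no capture condition. If an aggregate is meant, the protocol should say so, and say whether it is averaged or pooled.

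Three stronger inferences are tempting and should not be drawn.

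- A reader might infer that only about a quarter of services would meet the rule. That follows from assuming symmetry around 60%; nothing in the protocol fixes the spread.
- A reader might infer that commissioning as the NHS-standard platform follows from the primary outcome. Section 6.2.1 ties it to gathering adequate data, and the aim names both conditions.
- A reader might take the 80% target to require every key block to be complete for a patient. No section says so. Section 4 can be read as 80% of patients having each variable.

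On the questionnaire interval, the outcome table and Appendix 2 agree with section 4, and the 6-month sentence stands alone in the data-management text. That makes it easy to reconcile, but the contradiction remains in the current protocol.

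**Conclusion.** The mismatch is real and lies in the current text, not in detail that could be left to an analysis plan. Meeting the primary and secondary targets does not imply that half of services each capture 60% of their patients. With 25 of 49 services in use and a mean of exactly 60%, between 1 and 25 services qualify. The mid-range figure of about 26% is a scenario. The full range needs no assumption beyond the service count and the mean. The conclusion that the aim can be missed rests on the per-service reading. The absence of any capture condition in the primary outcome does not. The averaged-or-pooled ambiguity, the differing 80% wordings and the conflicting questionnaire intervals are separate smaller defects, each of which can change the reported result.

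**What to change.** 1. Make the success measure the number and percentage of services that each capture data on at least 60% of their unique attenders between site opening and month 24, divided by a fixed, dated list of services, with a target of 50%. Site opening dates will differ, so report each service's window.
2. Report any use of the system as a process measure, and give the pooled capture percentage alongside.
3. If an aggregate 60% is intended instead, say so in section 3, state whether it is averaged or pooled, and attach the capture condition to the success measure.
4. State the 80% target in one form in sections 3.2, 4 and 6.2.1: for example, key items entered divided by key items due, with per-variable percentages as description.
5. Reconcile the questionnaire interval in section 7.6 with sections 3.2 and 4 and Appendix 2, so that the number of entries possible has one definition.

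The cost is protocol wording. The capture formula already needs each clinic's attendance count, so no new data are required. The downside is that success becomes harder to reach.
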